#### Management of Enrolled Participants with Detectable HBV DNA During the Study

If HBV DNA is detected, IP will be temporarily withheld or study treatment will be permanently discontinued, as described in [Section 7.1.2](#) and [Section 7.2.1](#), respectively, and the participant should be referred for appropriate follow-up medical care.

#### Hepatitis C Testing

As specified in the SoA ([Table 1-1](#)), initial testing for HCV infection includes testing for antibodies to HCV (anti-HCV).

- If anti-HCV is positive, a test for circulating HCV RNA is required.
- If HCV RNA test is negative, the participant is not excluded.
- If HCV RNA test is positive, the participant is excluded ([Section 5.2](#)).

Participants who have had HCV infection and have been successfully treated, defined as a sustained virologic response (HCV RNA by polymerase chain reaction negative for at least 24 weeks following treatment completion), are not excluded on the basis of HCV as long as HCV RNA test is negative at screening.

If HCV RNA is detected during the study, the study treatment will be discontinued ([Section 7.1](#)), and the participant should receive appropriate follow-up medical care.

### 8.3.7.7 Hepatic Safety Monitoring, Evaluation, and Criteria for Investigational Product Interruption or Discontinuation

Table 8-1 and Table 8-2 summarize actions to take based on abnormal hepatic laboratory or clinical changes.

**Table 8-1 Participants with Normal or Near Normal Baseline (ALT, AST, or ALP <1.5 × ULN)**

If this laboratory value is observed...	Then...		
	Initiate or continue close hepatic monitoring	Initiate comprehensive evaluation	Interrupt or discontinue IP
ALT or AST $\geq 3 \times$ ULN	X		
ALP $\geq 2 \times$ ULN	X		
TBL $\geq 2 \times$ ULN b	X		
ALT or AST $\geq 5 \times$ ULN	X	X	
ALP $\geq 2.5 \times$ ULN	X	X	
ALT or AST $\geq 3 \times$ ULN with hepatic signs or symptoms a	X	X	X
ALT or AST $\geq 5 \times$ ULN for more than 2 weeks	X	X	X
ALT or AST $\geq 8 \times$ ULN	X	X	X
ALT or AST $\geq 3 \times$ ULN and TBL $\geq 2 \times$ ULN b or INR $\geq 1.5$	X	X	X
ALP $\geq 3 \times$ ULN	X	X	X
ALP $\geq 2.5 \times$ ULN and TBL $\geq 2 \times$ ULN b	X	X	X
ALP $\geq 2.5 \times$ ULN with hepatic signs or symptoms a	X	X	X

Abbreviations: ALP = alkaline phosphatase; ALT = alanine aminotransferase; AST = aspartate aminotransferase; INR = international normalized ratio; IP = investigational product; TBL = total bilirubin; ULN = upper limit of normal.

a Examples of hepatic signs or symptoms: severe fatigue, nausea, vomiting, right upper quadrant abdominal pain, fever, and/or rash.

b In participants with Gilbert’s syndrome the threshold for TBL may be higher.

**Table 8-2 Participants with Elevated Baseline (ALT, AST, or ALP  $\geq 1.5 \times$  ULN)**

If this laboratory value is observed...	Then...		
	Initiate or continue close hepatic monitoring	Initiate comprehensive evaluation	Interrupt or discontinue IP
ALT or AST $\geq 2 \times$ baseline	X		
ALP $\geq 2 \times$ baseline	X		
TBL $\geq 2 \times$ ULN b	X		
ALT or AST $\geq 3 \times$ baseline or $\geq 250$ U/L (whichever occurs first)	X	X	
ALP $\geq 2.5 \times$ baseline	X	X	
ALT or AST $\geq 2 \times$ baseline or $\geq 250$ U/L (whichever occurs first) with hepatic signs or symptoms a	X	X	X
ALT or AST $\geq 3 \times$ baseline or $\geq 250$ U/L (whichever occurs first) for more than 2 weeks	X	X	X
ALT or AST $\geq 4 \times$ baseline or $\geq 400$ U/L (whichever occurs first)	X	X	X
ALT or AST $\geq 2 \times$ baseline or $\geq 250$ U/L (whichever occurs first) and TBL $\geq 2 \times$ ULN b or INR $\geq 1.5$	X	X	X
ALP $\geq 3 \times$ baseline	X	X	X
ALP $\geq 2.5 \times$ baseline and TBL $\geq 2 \times$ ULN b	X	X	X
ALP $\geq 2.5 \times$ baseline with hepatic signs or symptoms a	X	X	X

Abbreviations: ALP = alkaline phosphatase; ALT = alanine aminotransferase; AST = aspartate aminotransferase; INR = international normalized ratio; IP = investigational product; TBL = total bilirubin; ULN = upper limit of normal.

a Examples of hepatic signs or symptoms: severe fatigue, nausea, vomiting, right upper quadrant abdominal pain, fever, and/or rash.

b In participants with Gilbert’s syndrome the threshold for TBL may be higher.

### 8.3.7.8 Close Hepatic Monitoring

If a participant develops any one of these changes, initiate close hepatic monitoring (Table 8-3).

**Table 8-3 Close Hepatic Monitoring**

Participants with normal or near normal baseline (ALT, AST, or ALP < 1.5 × ULN)	Participants with elevated baseline (ALT, AST, or ALP ≥ 1.5 × ULN)
ALT or AST ≥ 3 × ULN or	ALT or AST ≥ 2 × baseline
ALP ≥ 2 × ULN or	ALP ≥ 2 × baseline
TBL ≥ 2 × ULN a	TBL ≥ 2 × ULN a

Abbreviations: ALP = alkaline phosphatase; ALT = alanine aminotransferase; AST = aspartate aminotransferase; TBL = total bilirubin; ULN = upper limit of normal.

a In participants with Gilbert’s syndrome, the threshold for TBL may be higher.

Close hepatic monitoring should include these actions:

- Laboratory tests ([Appendix 15.2](#)), including alanine aminotransferase, aspartate aminotransferase, alkaline phosphatase, total bilirubin, direct bilirubin, gamma-glutamyl transferase, creatine kinase, and complete blood count with differential, should be checked within 48 to 72 hours of the detection of elevated liver tests to confirm the abnormality and to determine if it is increasing or decreasing.
- If the abnormality persists, clinical and laboratory monitoring should continue at a frequency of 2 to 3 times weekly until levels normalize or return to approximate baseline values.
- In younger adolescents, special care should be taken to minimize the volume of blood taken during hepatic monitoring.
- In addition to the laboratory tests, basic evaluation for possible causes of abnormal liver tests should be initiated by the investigator in consultation with the Lilly-designated medical monitor. At a minimum, this evaluation should include physical examination and a thorough medical history, including current symptoms, recent illnesses (eg, heart failure, systemic infection, hypotension, or seizures), recent travel, concomitant medications (including over-the-counter), herbal and dietary supplements, and history of alcohol drinking and other substance abuse.

### 8.3.7.9 Comprehensive Hepatic Evaluation

If a participant develops any one of the following laboratory or clinical changes, initiate a comprehensive hepatic evaluation ([Table 8-4](#)).

**Table 8-4 Comprehensive Hepatic Evaluation**

Participants with normal or near normal baseline (ALT, AST, or ALP <1.5 × ULN)	Participants with elevated baseline (ALT, AST, or ALP ≥1.5 × ULN)
ALT or AST ≥5 × ULN or	ALT or AST ≥3 × baseline or ≥250 U/L (whichever occurs first) or
ALP ≥2.5 × ULN or	ALP ≥2.5 × baseline or
ALT or AST ≥3 × ULN with hepatic signs or symptoms a or	ALT or AST ≥2 × baseline or ≥250 U/L (whichever occurs first) with hepatic signs or symptoms a or
ALT or AST ≥5 × ULN for more than 2 weeks or	ALT or AST ≥3 × baseline or ≥250 U/L (whichever occurs first) for more than 2 weeks or
ALT or AST ≥8 × ULN or	ALT or AST ≥4 × baseline or ≥400 U/L (whichever occurs first) or
ALT or AST ≥3 × ULN and TBL ≥2 × ULN b or INR ≥ 1.5	ALT or AST ≥2 × baseline or ≥250 U/L (whichever occurs first) and TBL ≥2 × ULN b or INR ≥ 1.5

Abbreviations: ALP = alkaline phosphatase; ALT = alanine aminotransferase; AST = aspartate aminotransferase; INR = international normalized ratio; TBL = total bilirubin; ULN = upper limit of normal.

- a Examples of hepatic signs or symptoms: severe fatigue, nausea, vomiting, right upper quadrant abdominal pain, fever, and/or rash.
- b In participants with Gilbert’s syndrome the threshold for TBL may be higher.

Comprehensive hepatic evaluation should include these actions:

- At a minimum, comprehensive hepatic evaluation should include physical examination and a thorough medical history, as outlined above, as well as tests for prothrombin time-international normalized ratio; tests for viral hepatitis A, B, C, and E; tests for autoimmune hepatitis; and an abdominal imaging study (eg, ultrasound or CT scan).
- Based on the participant’s history and initial results, further testing should be considered in consultation with the Lilly-designated medical monitor, including tests for hepatitis D virus, cytomegalovirus, Epstein-Barr virus, acetaminophen levels, acetaminophen protein adducts, urine toxicology screen, Wilson’s disease, blood alcohol levels, urinary ethyl glucuronide, and blood phosphatidylethanol.
- Based on the circumstances and the investigator’s assessment of the participant’s clinical condition, the investigator should consider referring the participant for a hepatologist or gastroenterologist consultation, and additional tests including magnetic resonance cholangiopancreatography, endoscopic retrograde cholangiopancreatography, cardiac echocardiogram, or a liver biopsy.

- Clinical and laboratory monitoring should continue at a frequency of 1 to 3 times weekly until levels normalize or return to approximate baseline values.
- All the medical information and tests results related to the hepatic monitoring and comprehensive hepatic evaluation tests should be collected and recorded on the hepatic safety page in the eCRF.

### 8.3.7.10 Investigational Product Interruption or Discontinuation

If a participant develops any one of the following laboratory or clinical changes, interrupt the IP and continue close monitoring and comprehensive hepatic evaluation as described in [Table 8-5](#), [Section 8.3.7.7](#), and [Section 8.3.7.8](#).

**Table 8-5 Laboratory or Clinical Changes Resulting in Investigational Product Interruption or Discontinuation**

Participants with normal or near normal baseline (ALT, AST, or ALP <1.5 × ULN)	Participants with elevated baseline (ALT, AST, or ALP ≥1.5 × ULN)
ALT or AST ≥3 × ULN with hepatic signs or symptoms a or	ALT or AST ≥2 × baseline or ≥250 U/L (whichever occurs first) with hepatic signs or symptoms a or
ALT or AST ≥5 × ULN for more than 2 weeks or	ALT or AST ≥3 × baseline or ≥250 U/L (whichever occurs first) for more than 2 weeks or
ALT or AST ≥8 × ULN or	ALT or AST ≥4 × baseline or ≥400 U/L (whichever occurs first) or
ALT or AST ≥3 × ULN and TBL ≥2 × ULN b or INR ≥ 1.5 or	ALT or AST ≥2 × baseline or ≥250 U/L (whichever occurs first) and TBL ≥2 × ULN b or
ALP ≥3 × ULN or	ALP ≥3 × baseline or
ALP ≥2.5 × ULN and TBL ≥2 × ULN b or	ALP ≥2.5 × baseline and TBL ≥2 × ULN b or
ALP ≥2.5 × ULN with hepatic signs or symptoms a	ALP ≥2.5 × baseline with hepatic signs or symptoms a

Abbreviations: ALP = alkaline phosphatase; ALT = alanine aminotransferase; AST = aspartate aminotransferase; INR = international normalized ratio; TBL = total bilirubin; ULN = upper limit of normal.

a. Examples of hepatic signs or symptoms: severe fatigue, nausea, vomiting, right upper quadrant abdominal pain, fever, and/or rash.

b. In participants with Gilbert’s syndrome the threshold for TBL may be higher.

Interruption or discontinuation of IP should include these actions:

- While the participant is not receiving the IP, clinical and laboratory monitoring should continue at a frequency of 1 to 3 times weekly until liver tests normalize or return to approximate baseline values.

- If the hepatic event continues past the anticipated end of the study (ie, data lock) the investigator should consult with the Lilly-designated medical monitor to determine the need for further data collection beyond the end date of the study (ie, data lock date).
- All the medical information and test results related to the close hepatic monitoring ([Section 8.3.7.8](#)) and comprehensive hepatic evaluation ([Section 8.3.7.9](#)) should be collected and recorded on the hepatic safety page in the eCRF.
- Resumption of the IP after interruption for a hepatic reason can be considered only in consultation with the Lilly-designated medical monitor and only if the liver test results returned to near baseline and if a self-limited non-IP etiology is identified. Otherwise, the IP should be permanently discontinued.

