### **7.1.1 Liver Chemistry Stopping Criteria**

Refer to [Section 8.3.7.7](#) for hepatic criteria for IP interruption or discontinuation.

Discontinuation of IP because of clinically significant abnormal liver test results should be considered by the investigator in consultation with the medical monitor when a participant meets one of the conditions presented in [Section 7.1](#), or in the presence of abnormal liver chemistries not meeting protocol-specified stopping rules if the investigator believes that it is in best interest of the participant.

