## 15.4 Clinical Laboratory Tests

General guidance for clinical laboratory testing ([Table 15-1](#)) includes the following:

- The tests detailed in the table below will be performed by the central laboratory.
- In circumstances where the sponsor approves local laboratory testing in lieu of central laboratory testing (in the table below), the local laboratory must be qualified in accordance with applicable local regulations.
- Protocol-specific requirements for inclusion or exclusion of participants are detailed in [Section 5](#) of the protocol.
- Additional tests may be performed at any time during the study as determined necessary by the investigator or required by local regulations.
- Investigators must document their review of the laboratory safety results.

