**Table 15-1 Clinical Laboratory Tests**

Clinical Laboratory Tests	Comments
Hematology	Assayed by the central laboratory.
Hemoglobin	
Hematocrit	
Erythrocyte count (RBCs)	
Mean cell volume	
Mean cell hemoglobin	

Clinical Laboratory Tests	Comments
Mean cell hemoglobin concentration	
Leukocytes (WBCs)	
Differential	
Percent and absolutes count of:	
Neutrophils, segmented	
Neutrophils, bands	
Lymphocytes	
Monocytes	
Eosinophils	
Basophils	
Platelets	
Cell morphology (RBCs and WBCs)	
Absolute neutrophil count (Calculation) (Definition - include segs and bands or segs, bands, and other immature cells)	
Clinical Chemistry	Assayed by the central laboratory.
Sodium	
Potassium	
Chloride	
Bicarbonate	
Total bilirubin	
Direct bilirubin	
Alkaline phosphatase	
Alanine aminotransferase	
Aspartate aminotransferase	
Gamma-glutamyl transferase	
Blood urea nitrogen	
Creatinine	
Creatine kinase	
Uric acid	
Total protein	
Albumin	
Calcium	
Phosphorus	
Glucose (nonfasting)	

Clinical Laboratory Tests	Comments
Hormones (female)	
Serum pregnancy	Assayed by the central laboratory.
Urine pregnancy	Evaluated locally.
HIV and Hepatitis Serology	Assayed by the central laboratory.
HIV testing	
HCV testing:	
HCV antibody	
HCV RNA	Performed only for participants who test positive for HCV antibody.
HBV testing:	
HBV DNA	Performed only for participants who test positive for HBcAb.
HBcAb	
HBsAg	
HBsAb	
Pharmacokinetic Samples	Assayed by Lilly-designated laboratory. Results will not be provided to the study sites.
LY3650150 concentration	
Immunogenicity Samples	Assayed by Lilly-designated laboratory. Results will not be provided to the study sites.
Anti-LY3650150 antibodies	
Anti-LY3650150 antibodies neutralization	
Genetics Sample	Assayed by Lilly-designated laboratory. Results will not be provided to the study sites.
Exploratory Biomarker Sample	Assayed by Lilly-designated laboratory. Results will not be provided to the study sites.
Whole blood	
Plasma	
Serum	
Nasal brushing	
Hypersensitivity Tests and/or Infusion-Related Reaction (as appropriate)	Assayed by the central laboratory. Results will not be provided to the study sites.
Hepatic Monitoring	Assayed by the central laboratory. Results will not be provided to the study sites.
Hepatic Monitoring	Assayed by central laboratory. Results will not be provided to the study sites.

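### Table 8-5 drops INR ≥1.5 as a reason to interrupt IP in participants with elevated baseline liver tests, although Table 8-2 requires it

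*Protocol*

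**What the plan says.** The hepatic rules are set out more than once. In Section 8.3.7.7, Tables 8-1 (normal or near-normal baseline) and 8-2 (elevated baseline) match laboratory findings to three actions: close monitoring, comprehensive evaluation, and interruption or discontinuation of IP. Sections 8.3.7.8 to 8.3.7.10 then restate the triggers for each action in Tables 8-3, 8-4 and 8-5.

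Section 8.3.7.10 introduces Table 8-5 with "If a participant develops any one of the following laboratory or clinical changes, interrupt the IP and continue close monitoring" and cites Table 8-5, Section 8.3.7.7 and Section 8.3.7.8 together. In its elevated-baseline column the combined criterion is "ALT or AST ≥2 × baseline or ≥250 U/L (whichever occurs first) and TBL ≥2 × ULN", with no INR alternative. The corresponding row of Table 8-2 accepts either TBL ≥2 × ULN or INR ≥1.5 and is marked for all three actions, including interruption.

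Section 7.1.1 sends the reader to Section 8.3.7.7 "for hepatic criteria for IP interruption or discontinuation". It does not mention Table 8-5.

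On access to results, both Hepatic Monitoring rows of Table 15-1 carry the comment "Assayed by the central laboratory. Results will not be provided to the study sites" (the second row differs by one word). Section 15.4, which contains that table, also states "Investigators must document their review of the laboratory safety results".

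**The concern.** This is a stopping rule. Raised aminotransferases with INR ≥1.5 are a reason to hold IP for participants with normal baseline tests in both places where the rule appears. For those with elevated baseline tests they are a reason in Table 8-2 but not in Table 8-5. Table 8-5 does not tell the site to continue dosing; it leaves out a trigger. A site that reads Table 8-2 holds IP, while a site working from Table 8-5 is not told to.

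The omission affects only participants who enter with abnormal liver tests. A missed hold also bypasses the conditions for restarting IP in Section 8.3.7.10: medical-monitor consultation, liver tests back near baseline, and an identified self-limited cause other than IP. The study has no external data monitoring committee (Section 9.9), so the criteria applied at the site matter.

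The Table 15-1 comment adds to the problem. Read literally, it keeps central hepatic follow-up results, INR among them, from the person who must apply the rule.

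**Working it through.** No sample size, power or alpha figure is involved. The check compares the tables and then asks whether the gap can occur in practice.

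**1. The criterion in its six places**

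| Place | ALT/AST limb | INR ≥1.5 accepted? |
|---|---|---|
| Table 8-1 (normal baseline) | ≥3 × ULN | yes |
| Table 8-2 (elevated baseline) | ≥2 × baseline or ≥250 U/L | yes |
| Table 8-4, normal column | ≥3 × ULN | yes |
| Table 8-4, elevated column | ≥2 × baseline or ≥250 U/L | yes |
| Table 8-5, normal column | ≥3 × ULN | yes |
| Table 8-5, elevated column | ≥2 × baseline or ≥250 U/L | **no** |

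The limb is present in 5 of 6. Comparing all interruption rows, Tables 8-1 and 8-5 agree on 7 of 7, and Tables 8-2 and 8-5 on 6 of 7.

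**2. Would INR be measured?** The tests named for close monitoring in Section 8.3.7.8 end with "creatine kinase, and complete blood count with differential, should be checked within 48 to 72 hours of the detection of elevated liver tests" and do not include INR. The minimum content of the comprehensive evaluation in Section 8.3.7.9 does include it: "tests for prothrombin time-international normalized ratio". For elevated-baseline participants that evaluation starts at ALT/AST ≥3 × baseline or ≥250 U/L, or at ALP ≥2.5 × baseline.

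**3. Where the tables disagree.** With INR ≥1.5, Table 8-2 interrupts and Table 8-5 does not when TBL <2 × ULN, there are no hepatic symptoms, ALP <3 × baseline, the elevation has lasted 2 weeks or less, and ALT/AST is below the 4 × baseline or 400 U/L row. If ALT/AST itself triggers the INR test, the range is

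min(3 × baseline, 250) ≤ ALT < min(4 × baseline, 400).

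| Baseline ALT (U/L) | Lower bound | Upper bound (not included) |
|---|---|---|
| 45 | min(135, 250) = 135 | min(180, 400) = 180 |
| 60 | min(180, 250) = 180 | min(240, 400) = 240 |
| 80 | min(240, 250) = 240 | min(320, 400) = 320 |
| 100 | min(300, 250) = 250 | min(400, 400) = 400 |
| 160 | min(480, 250) = 250 | min(640, 400) = 400 |

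A small further region is ALT/AST at 2 to <3 × baseline (and below 250 U/L) when ALP at 2.5 to <3 × baseline has triggered the evaluation.

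**4. Worked case** (ULN 40 U/L assumed). Baseline ALT is 80 U/L (2 × ULN). On treatment: ALT 280 U/L, INR 1.6, TBL 1.2 × ULN, ALP normal, no symptoms, first detection.

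- 280/80 = 3.5 × baseline, so the evaluation and the INR test are triggered.
- Table 8-2: ALT ≥2 × baseline with INR ≥1.5 is met, so IP is interrupted.
- Table 8-5, elevated column: 280 is below 4 × 80 = 320 and below 400; TBL is below 2 × ULN; there are no symptoms; 2 weeks have not passed; the ALP rows are not met. No row applies.

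**5. How long the gap lasts.** Table 8-5 also interrupts for ALT/AST ≥3 × baseline or ≥250 U/L lasting more than 2 weeks, so a sustained elevation is eventually caught. If ALT/AST falls to 2 to <3 × baseline and below 250 U/L while INR stays ≥1.5, that row does not apply, although Table 8-2 still does.

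**6. Doses within 14 days of detection.** The Schedule of Activities draws on-treatment chemistry at Weeks 4, 8, 16, 24, 40 and 56. From Table 6-2, the next injection after Weeks 4, 8 and 16 is at Weeks 6, 10 and 18, that is, day 14: one 250 mg dose. From Table 6-3, the next injection after Weeks 24 and 40 is at Weeks 28 and 44, day 28: none within 14 days. No dose is given at Week 56.

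**7. Access to results.** Section 8.3.7.8 has abnormal tests repeated and followed. Section 8.3.7.9 says "tests results related to the hepatic monitoring and comprehensive hepatic evaluation tests should be collected and recorded on the hepatic safety page" of the eCRF, and Section 8.3.7.10 has a similar instruction. Appendix 15.2 expects results to be reported where a validated test exists and permits additional local testing. The withholding comment in Table 15-1 is the outlier.

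**The case against.** The strongest reply is that the protocol largely resolves the matter. Section 7.1.1, which is headed as the liver stopping criteria, points to Section 8.3.7.7, as does Section 7.1.2 for liver test abnormalities. Section 8.3.7.7 contains Table 8-2 with the INR limb. The lists are any-one-of triggers, so a site applying every table would hold IP. On this view Table 8-5 is an incomplete repeat, not an opposing instruction. That is good evidence of the intended rule and settles the direction of the correction. It is still a pointer and not a precedence statement, and Table 8-5 is the list directly beneath the instruction to interrupt.

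Second, other safeguards act in the meantime. Table 8-4 still triggers the evaluation, monitoring runs 1 to 3 times weekly, the medical monitor is consulted on further testing, and Section 7.1.1 allows discontinuation when no stopping rule is met. All of this stands and limits the harm. Discretion does not replace a stated threshold, however.

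Third, the exposure is small: at most one dose for abnormalities found at scheduled induction visits and none within two weeks for those found at Weeks 24 or 40. This is accepted for sustained elevations.

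Fourth, the Table 15-1 comment is a separate matter. That is fair. The routine ALT, AST, ALP and bilirubin rows of that table carry no such comment, so the point is secondary and adds no weight to the INR omission.

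**Conclusion.** The concern holds. The elevated-baseline cell of Table 8-5 omits a trigger that Table 8-2 marks for interruption and that appears in the other five statements of the criterion, and nothing ranks the tables. The mismatch can arise with protocol-required testing, for instance at ALT 240 to <320 U/L for a baseline of 80 U/L, or 250 to <400 U/L for a baseline of 100 U/L.

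If ALT/AST stays at or above the lower of 3 × baseline and 250 U/L, the hold comes up to about two weeks late, or one 250 mg dose in induction. If ALT/AST falls below that level with INR still raised, Table 8-5 gives no hold on the two-week row.

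The document does not give the number of participants affected. It is likely small, since known cirrhosis, chronic hepatitis and laboratory abnormalities judged clinically significant are excluded (Section 5.2). Power, Type I error and the estimand are unaffected. The worked case assumes an ALT ULN of 40 U/L; the ranges expressed as multiples of baseline do not depend on that. It remains a wrong threshold in operative safety text and should be corrected.

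**What to change.** Add the INR ≥1.5 alternative to the elevated-baseline cell of Table 8-5 that combines ALT/AST with TBL, so that it matches Tables 8-2 and 8-4 and the normal-baseline column of the same row.

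As a secondary change, delete the statement that results are not given to sites from the two Hepatic Monitoring rows of Table 15-1.

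The cost is one table cell and two table comments in the next amendment, with a clarification letter to sites until then. No procedures, visits or participants are added.

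### Minimum liver-test frequency is 2 per week at the mildest hepatic step but 1 per week at the more severe steps, although the same participants fall under both instructions

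*Protocol*

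**What the plan says.** The hepatic safety rules in Section 8.3.7 of the Protocol have three cumulative steps, each with a monitoring frequency.

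- **Close hepatic monitoring (8.3.7.8, under Table 8-3).** A recheck within 48 to 72 hours comes first. For an abnormality that has not resolved, the instruction then reads: "clinical and laboratory monitoring should continue at a frequency of 2 to 3 times weekly until levels normalize or return to approximate baseline values".
- **Comprehensive hepatic evaluation (8.3.7.9, under Table 8-4).** "Clinical and laboratory monitoring should continue at a frequency of 1 to 3 times weekly until levels normalize or return to approximate baseline values".
- **IP interruption or discontinuation (8.3.7.10, under Table 8-5).** "While the participant is not receiving the IP, clinical and laboratory monitoring should continue at a frequency of 1 to 3 times weekly", again until liver tests are normal or close to baseline.

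Tables 8-1 and 8-2 in Section 8.3.7.7 list the triggers for participants with normal and with elevated baseline values. The column headed "Initiate or continue close hepatic monitoring" is marked in every row of both tables. The lead sentence of 8.3.7.10 tells sites to "interrupt the IP and continue close monitoring and comprehensive hepatic evaluation as described in" other parts of the protocol; the places it names are Sections 8.3.7.8 and 8.3.7.7 and Table 8-5.

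**The concern.** A participant who reaches the second or third step is still under close monitoring, so two instructions apply at once: at least 2 checks per week from Section 8.3.7.8, and at least 1 from Section 8.3.7.9 or 8.3.7.10. The lower minimum is the one printed at the more severe steps.

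What is at stake is the minimum safety follow-up of participants with the worse liver tests, which depends on which paragraph the site reads. Under 8.3.7.9 this includes participants with ALT or AST at 5 x ULN or above who are still being dosed. In them the site must also judge the rule that stops IP once that level has lasted more than 2 weeks. Under 8.3.7.10 it concerns follow-up to recovery after IP is stopped, which also informs any decision to resume, because resumption requires tests near baseline.

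**Working it through.** The plan states no derived figure on this point, so there is none to reproduce. The check is a comparison of the texts and a count of table rows.

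**1. The three instructions side by side**

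| Section | Step | Minimum per week | Maximum per week | Continues until |
|---|---|---|---|---|
| 8.3.7.8 | Close monitoring | 2 | 3 | normal or near baseline |
| 8.3.7.9 | Comprehensive evaluation | 1 | 3 | normal or near baseline |
| 8.3.7.10 | IP interrupted or stopped | 1 | 3 | normal or near baseline |

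The end condition is essentially the same in all three, so they run concurrently and are not successive phases. None makes the lower frequency conditional on falling values.

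**2. Who falls under more than one instruction**

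Tables 8-1 and 8-2 have the same structure:

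| Actions marked | Table 8-1 | Table 8-2 | Both |
|---|---|---|---|
| Close monitoring only | 3 | 3 | 6 |
| Plus comprehensive evaluation, IP continues | 2 | 2 | 4 |
| Plus IP interruption or discontinuation | 7 | 7 | 14 |
| Total | 12 | 12 | 24 |

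Close monitoring is marked in 12 of 12 rows of each table. Rows that carry both minimums: 4 + 14 = 18 of 24. Rows with the 2-per-week minimum alone: 6 of 24, and these are the mildest triggers.

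**3. Direction of the difference**

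For a participant with normal baseline and IP continuing, ALT or AST at 3 x ULN falls under 8.3.7.8 alone, with a minimum of 2 per week. At 5 x ULN the action list of 8.3.7.9 prints a minimum of 1. At 8 x ULN, with IP stopped, 8.3.7.10 also prints 1. Stopping the drug might explain a lower minimum in 8.3.7.10. It cannot explain the one in 8.3.7.9, where 4 rows keep the participant on IP.

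**4. Size at the stated minimums**

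- Over 4 weeks: 2 x 4 = 8 checks versus 1 x 4 = 4.
- Over a 2-week window, relevant to participants still on IP: 2 x 2 = 4 versus 1 x 2 = 2.
- Average spacing: 7/2 = 3.5 days versus 7/1 = 7 days. The protocol fixes no spacing within the week.

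**The case against.** The strongest reply is that the steps are cumulative and the protocol largely answers the question itself. Close monitoring is marked in every row, and 8.3.7.10 sends the site back to 8.3.7.8, so the 2-per-week minimum travels with the participant. A range of 1 to 3 contains 2 to 3, and a site that checks 2 to 3 times weekly complies with everything. This supports 2 per week as the better reading. It does not remove the conflict, because no sentence ranks the two frequencies, and a site following only the action list of 8.3.7.9 or 8.3.7.10 can believe that once weekly is enough.

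A second reply is that overall follow-up does rise with severity: the later steps add INR, viral and autoimmune tests, imaging, possible specialist referral and then IP interruption, with the medical monitor consulted. That is correct; only one printed lower bound goes the wrong way.

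A third reply limits the consequence. The 18 of 24 counts table rows, which are nested, and not participants. The documents give no event rate. The checks-per-week figures assume a site that stays at the minimum. Weekly values can still be used to assess the rule on elevation lasting more than 2 weeks, and values at 8 x ULN, hepatic symptoms, or raised bilirubin or INR alongside raised transaminases stop IP without waiting. All of this stands, and it keeps the point from being more serious than a correction that should be made.

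Finally, a fixed minimum of 2 draws per week during slow recovery sits uneasily with the instructions in 8.3.7.8 and Appendix 15.4 to limit blood volume during hepatic monitoring. That bears on the form of the fix and not on whether one is needed.

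**Conclusion.** The inconsistency is real and lies in the current protocol text. In 18 of 24 trigger rows (9 of 12 in each table; 4 with IP continuing, 14 with IP stopped) two minimums apply, 2 and 1 checks per week, and the lower one is printed at the more severe steps. The conflict concerns the minimum only; the maximum is 3 throughout.

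This rests on reading the tables as they are marked, with close monitoring continuing at every step, which the lead sentence of 8.3.7.10 confirms. The document does not show which frequency was intended. The recheck at 48 to 72 hours is unaffected, and no effect is claimed on power, error control, the efficacy analysis or the rate of permanent discontinuation. Few participants are likely to be involved. It should be corrected because it sets the safety follow-up of those with the worst liver tests.

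**What to change.** Replace 1 to 3 with 2 to 3 times weekly in the action lists of Sections 8.3.7.9 and 8.3.7.10, so that all three sections agree.

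Alternatively, write an explicit step-down rule that applies across the three sections, for example once weekly only after values are confirmed to be declining. The stated minimum then never falls as severity rises. This version also limits blood draws during slow recovery, including in younger adolescents.

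While editing, add Section 8.3.7.9 to the cross-references in the lead sentence of 8.3.7.10, which asks for comprehensive evaluation to continue but points only to Table 8-5 and Sections 8.3.7.7 and 8.3.7.8.

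The cost is a wording correction in the next amendment or a clarification letter, and a few extra draws in the rare participants affected, which Section 8.3.7.8 already requires.
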